2.4.5.1.3 Sensitivity analyses

The primary analysis will also be performed according to each reader, respectively.

The primary analysis will be repeated in the PP population.

2.4.5.2 Analyses of secondary endpoints

Analysis of secondary endpoints will be performed primarily on the mITT population and may be performed on the PP population.

Relative decrease from baseline in Ki67 ≥50%

The proportion of participants with a relative decrease from baseline in Ki67 ≥50% (ie $(\text{Ki67}_{\text{pre}} - \text{Ki67}_{\text{post}}) / \text{Ki67}_{\text{pre}} \geq 50\%$) will be provided for each treatment arm along with the 95% CI computed using the Clopper-Pearson method.

Logistic regression will be used with a 50% decrease in Ki67 as the response variable to determine potential factors (as defined in [Table 4](#)) that are predictive and/or prognostic for the disease. A multivariable logistic regression model will be conducted using a stepwise selection procedure with a 15% significance level for removing effects.

ER degradation by protein expression

ER expression in H-score before and after treatment, the absolute change from baseline (defined as $ER\ H\text{-score}_{\text{post}} - ER\ H\text{-score}_{\text{pre}}$) as well as the relative change from baseline (defined as $100 \times (\text{absolute change from baseline} / ER\ H\text{-score}_{\text{pre}})$) will be summarized for each arm. In case differences on baseline ER H-score are observed, additional ANCOVA model on the absolute change from baseline adjusted for baseline may be performed. In that case, LS-means of the absolute change from baseline and associated 95% CI will be provided.

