1.3 DETERMINATION OF SAMPLE SIZE

The sample size is determined based on the following assumptions:

- The geometric mean of percentage reduction in Ki67 after a 14-day treatment period for the control arm is assumed to be 70% (1, 2, 3).
- The geometric mean of reduction in Ki67 after a 14-day treatment period is increased to 85% for each SAR439859 arm. Therefore the geometric means of residual Ki67 (defined as one minus the geometric mean of reduction) are assumed to be 30% for the control arm and 15% for treatment arms, corresponding to a log fold difference of -0.693 ($\log(0.15) - \log(0.3)$) under the alternative hypothesis.
- The standard deviation of the log-fold change after a 14-day treatment period is assumed to be 1.

[figure not shown]
A total of 40 evaluable participants (where evaluable are defined as participants who have both baseline and post treatment available biopsies with Ki67 values) per treatment arm will be needed, in order to achieve 85% marginal power at the overall one-sided Type I error rate of 2.5% controlled with an Hochberg procedure, based on a one-sided t-test on the log-transformed data. The disjunctive power, ie, the probability to reject at least one null hypothesis, that the true log-fold change in Ki67 after a 14-day treatment period for both SAR439859 arms and the control arm are the same, is estimated at 91.5%.

Allowing for a 5% non-evaluable participant rate, the total sample size for randomization is 126 participants (42 per treatment arm).

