2.4.5.1.2 Subgroup analyses

Evaluation of consistency

The consistency of the results from the primary analysis will be evaluated across pre-defined subgroups in patients available in the subgroup of consideration. The subgroups included but not limited are defined in [Table 4](#). Depending upon the study results, additional subgroups may be examined, and subgroups with small sample sizes may be pooled to create a larger meaningful subgroup. For each subgroup, geometric LS-mean of percentage reduction in Ki67 with their associated 95% CIs and geometric LS-mean ratio of proportional change between treatment arms with their associated 95% CIs will be provided for each treatment arm.

Evaluation of interactions

For each pre-defined factor defined in [Table 4](#), log-fold change in Ki67 will be analyzed using linear regression model with terms for the factor, treatment and their interaction, adjusted by log baseline Ki67. The p-value of the test of interaction will be provided.

Other prognostic factors

Since the results from the primary analysis could be impacted by confounding factors, any potential issues will be examined and, if confirmed, exploratory analysis of the primary endpoint will be done accordingly. A multiple linear regression model will be used to identify prognostic factors among the demographic and baseline characteristics factors described in the [Table 4](#) using a stepwise selection procedure with a 15% significance level for removing effects. For significant prognostic factors identified in the multivariate model, the balance between treatment groups will be assessed.

Table 4 - Subgroup analyses

Prognostic factor	Description
Age	<65 years or ≥65 years
Race	Asian or White or Other
Tumor stage	1 or 2 or ≥ 3
Tumor size (greatest dimension)	≥10 mm to < 20mm, ≥ 20mm
Ki67 level at baseline (per central assessment)	<20% or ≥20%
ER H-score at baseline	Low ER+. (H-score 1-100) or moderate ER+ (H-score 101-200) or high ER+ (H-score 201-300).
Progesterone receptor	< 20% vs ≥20%

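### The stepwise logistic model for a 50% Ki67 decrease promises predictive factors but names no treatment or interaction term, so it supports prognostic association only

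*SAP*

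**What the plan says.** For the secondary endpoint of a Ki67 decrease of at least 50%, SAP 2.4.5.2 first plans a proportion per arm with a Clopper-Pearson interval. Protocol 9.4.1.2 plans only that. The SAP then adds a model: "Logistic regression will be used with a 50% decrease in Ki67 as the response variable to determine potential factors" from Table 4 "that are predictive and/or prognostic for the disease". The selection rule is: "A multivariable logistic regression model will be conducted using a stepwise selection procedure with a 15% significance level for removing effects".

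Table 4 lists age, race, tumor stage, tumor size, central baseline Ki67, baseline ER H-score and progesterone receptor. Treatment arm is not in it. SAP 2.4.5.2 names no forced-in term, no interaction and no comparison of factor effects between arms.

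For the continuous endpoint, SAP 2.4.5.1.2 keeps two questions apart. Effect modification is examined, one factor at a time, with a "linear regression model with terms for the factor, treatment and their interaction, adjusted by log baseline Ki67". A separate stepwise model has a narrower aim: "A multiple linear regression model will be used to identify prognostic factors among the demographic and baseline characteristics factors".

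**The concern.** A predictive factor is one across whose levels the treatment effect differs. Showing that requires a treatment contrast within each level and a comparison of those contrasts. A model holding baseline factors alone estimates how each factor relates to response, averaged over whatever arms are in the data. Fitting it separately by arm, which the SAP does not mention, would not settle the matter without a formal comparison between arms.

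The SAP recognises this distinction in 2.4.5.1.2. In 2.4.5.2 it uses the stepwise, prognostic type of model but adds the predictive claim. A factor retained at the 15% level could then be reported as predictive with no evidence that the drug effect depends on it, and a factor that truly modifies the effect could be missed.

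**Working it through.** **Inputs (SAP 1.3).** Geometric mean residual Ki67 is 30% on letrozole and 15% on each amcenestrant arm, "corresponding to a log fold difference of -0.693"; SD of the log-fold change is 1; 40 evaluable per arm.

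**The plan's own figure.** The SAP states "85% marginal power at the overall one-sided Type I error rate of 2.5% controlled with an Hochberg procedure" and 91.5% disjunctive power. Simulating two one-sided t-tests against a shared control with Hochberg (200,000 runs) gives 84.7% to 85.1% marginal and 91.6% to 91.7% disjunctive power. The design assumptions reproduce and are used below.

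**Implied response rates.** P(decrease ≥ 50%) = Φ(ln(0.5 / residual) / SD).
- Letrozole: Φ(ln(0.5/0.30)) = Φ(0.511) = 69.5%.
- Amcenestrant: Φ(ln(0.5/0.15)) = Φ(1.204) = 88.6%.
- Expected non-responders: 40 × 0.305 = 12.2 on letrozole and 40 × 0.114 = 4.6 on each amcenestrant arm, about 21 of 120 in total.

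**Two different factors, one pooled answer.** Take one binary factor with 50% prevalence. The prevalence and effect sizes here are assumptions, not figures from the documents.
- *Purely prognostic*: residual Ki67 differs 2-fold between levels in every arm (each arm's residual divided or multiplied by √2). Response is 80.4% against 56.5% on letrozole and 93.9% against 80.4% on amcenestrant. Averaged 1:2 over control and amcenestrant: (80.4 + 2 × 93.9)/3 = 89.4% against (56.5 + 2 × 80.4)/3 = 72.5%. Odds ratio 3.22.
- *Modifies the amcenestrant effect only*: letrozole residual 30% at both levels; amcenestrant residual 7.5% at one level and 30% at the other. Response is 69.5% at both levels on letrozole, and Φ(ln(0.5/0.075)) = 97.1% against 69.5% on amcenestrant. Averaged: (69.5 + 2 × 97.1)/3 = 87.9% against 69.5%. Odds ratio 3.19.

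A model without treatment terms sees practically the same odds ratio in both cases.

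**Simulation.** N = 120, 3,000 runs per scenario, likelihood-ratio tests at the 15% level. *Crossover* means response of 89.5% against 49.5% on letrozole and 78.6% against 98.6% on amcenestrant, which averages to 82.2% at both levels.

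| True factor | Kept by factor-only model | Flagged by factor-by-arm test |
|---|---|---|
| No effect | 16% | 22% |
| Purely prognostic | 84% | 20% |
| Modifies amcenestrant effect only | 87% | 83% |
| Crossover, no pooled effect | 12% | over 99% |

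The factor-only column does not separate the second row from the third, and it misses the fourth. The 22% and 20% in the right-hand column exceed the nominal 15%, so the ordinary likelihood-ratio interaction test is not well calibrated at this sample size.

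**Can interactions be fitted for this endpoint?** With evenly split factor levels and 40 per arm, the chance that at least one factor-by-arm cell has no non-responder is:
- Binary factor (20 per cell): 0.886^20 = 0.088 and 0.695^20 = 0.0007; 1 − (1 − 0.088)^4 × (1 − 0.0007)^2 = 31%.
- Three-level factor (13.3 per cell): 0.198 and 0.008; 1 − (1 − 0.198)^6 × (1 − 0.008)^3 = 74%.

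An empty cell gives separation and infinite estimates. The Table 4 main effects alone take 1+2+2+1+1+2+1 = 10 degrees of freedom against about 21 non-responders. SAP 2.4 says that enrollment ended early, so the actual numbers will be smaller.

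**The case against.** The best defence is that the wording is loose but little is lost. The 50% endpoint dichotomises the same Ki67 ratio that 2.4.5.1.2 analyses on the log scale, where interaction with treatment is tested for every Table 4 factor. That analysis uses more information than a binary repeat. The phrase in 2.4.5.2 joins the two terms with *and/or* and does not promise to separate them, and Table 4 heads its column with the word prognostic. All of this stands, and it limits the point to one analysis and one claim.

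Four stronger readings are tempting and should not be drawn.
- *The SAP excludes treatment from the model.* It is silent. It gives no equation and does not say that arms are pooled. The omission is inferred from the only covariates named and from the contrast with 2.4.5.1.2.
- *The linear stepwise model in 2.4.5.1.2 has the same flaw.* It claims prognostic factors only, and interactions are tested separately in that section.
- *The size of the problem is the omitted treatment odds ratio.* That ratio is (0.886/0.114)/(0.695/0.305) = 3.4, but it measures the arm effect and not the missing interaction. Under randomisation, leaving arm out mainly attenuates factor effects: an assumed within-arm factor odds ratio of 3 becomes about 2.8 when averaged over arms.
- *The model is meant to select patients.* The protocol's remarks on patient populations concern preoperative Ki67 trials in general. The endpoint's stated objective is the proportion in each arm, and no decision rule uses the logistic model.

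**Conclusion.** The point holds as a mismatch between aim and method in one exploratory analysis. The logistic model as specified in 2.4.5.2 supports statements of association with response. It does not support calling a factor predictive. In the illustration the factor-only model gave near-identical results for a prognostic factor and an effect modifier (odds ratios 3.22 and 3.19; kept in 84% and 87% of runs). A true modifier may well be retained; the model simply cannot show that it is one.

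The percentages rest on the SAP's residual Ki67 and SD assumptions, on the full 120 evaluable participants, and on one assumed binary factor rather than the seven-factor stepwise search. The conclusion that main effects alone cannot establish effect modification does not depend on them. The consequence is minor: what may be said about retained factors changes, while the primary analysis, the response proportions and the linear stepwise model are untouched.

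**What to change.** In SAP 2.4.5.2:
1. State that treatment arm is forced into the logistic model and is not subject to selection.
2. Delete the word *predictive* and report retained factors as prognostic associations.
3. Refer any statement about predictive factors to the factor-by-treatment interaction tests on log-fold change in 2.4.5.1.2.

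If an interaction on the binary endpoint is still wanted, fit one factor at a time with arm and factor-by-arm terms. Use a penalised (Firth) likelihood or pool the two amcenestrant arms, because ordinary maximum likelihood would often meet empty cells. Label the results exploratory and imprecise.

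The cost is a wording change, two degrees of freedom for arm, and a narrower claim. If the optional interactions are fitted with three arms, they add 2 × 10 = 20 degrees of freedom spread over seven separate models. No new data are needed.

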2.4.5.3 Additional analyses

Clinical response rate

ECOG response rate on each arm will be estimated by dividing the number of participants with clinical response (defined as clinical complete response (cCR), pathological complete response (pCR) or partial response (PR) as measured by ultrasound according to ECOG response criteria) by the number of participants from analysis population of the respective treatment arm. In addition, 95% two-sided CIs will be computed using the Clopper-Pearson method.

pCR rate

Pathological complete response rate on each randomized arm will be estimated by dividing the number of participants with complete pathological response (ie, no histologic evidence of invasive tumor cells in the surgical breast specimen and axillary nodes identified after neoadjuvant treatment) by the number of participants from the analysis population of the respective treatment arm. In addition, 95% two-sided CIs will be computed using the Clopper-Pearson method.

PEPI risk score

The total PEPI score, as defined in [Section 2.1.3.3](#), is the sum of the risk points derived from the pT stage, the pN stage, Ki67 levels and ER status of the surgical regimen. The total score after treatment will be summarized (quantitatively and by 3 risk categories: 0 (low risk), 1-3 (medium risk) and ≥ 4 (high risk)) for each treatment arm.

Complete cell cycle arrest (CCCA)

The proportion of participants with CCCA will be provided for each treatment arm along with the 95% CI computed using the Clopper-Pearson method.

Post-treatment Ki67 <10%

The proportion of participants with post-treatment Ki67 <10% will be provided for each treatment arm along with the 95% CI computed using the Clopper-Pearson method.

Ki67 by digital image-based method

The primary analysis defined in [Section 2.4.5.1.1](#) (except for ICC) will be performed on Ki67 results by digital image-based method.

2.4.6 Analyses of safety data

The summary of safety results will be presented by treatment group. All safety analyses will be performed on the safety population as defined in [Section 2.3.4](#). Safety data in patients who do not belong to the safety population (eg, exposed but not randomized) will be listed separately.

2.4.6.1 Analyses of adverse events

Generalities

The primary focus of adverse event reporting will be on treatment-emergent adverse events. Treatment emergent AEs are defined as AEs that develop, worsen (according to the Investigator's opinion), or become serious during the

- on treatment period (from first dose of IMP to last dose of IMP), or
- on treatment and post-treatment period (from first dose of IMP to last dose of IMP+30 days)

TEAE analyses will be produced for both analysis periods and therefore two sets of TEAEs tables will be generated. Pre-treatment adverse events will be described separately.

The severity grade will be taken into account in the summary. For patients with multiple occurrences of the same adverse event, the maximum (worst) grade by period of observation is used. Summaries will be provided for all grades and for grade ≥ 3 (including Grade 5). Missing grades, if any, will be included in the "all grades" category.

Sorting within tables ensures the same presentation for the set of all adverse events for each observation period (pre-treatment and treatment-emergent). For that purpose, the table of all treatment-emergent adverse events presented by SOC and PT sorted by the internationally agreed SOC order and decreasing frequency of PTs within SOC will define the presentation order for all other tables unless otherwise specified. Sorting will be based on the incidence of AEs of the SAR439859 400 mg QD arm.

Analysis of all treatment-emergent adverse events

The following TEAE summaries will be generated for the safety population.

- Overview of TEAEs, summarizing number (%) of patients with any

- Treatment emergent AEs
- Grade ≥ 3 TEAEs
- Grade 5 TEAE (any TEAE with a fatal outcome during the on-treatment period)
- Serious TEAEs
- Treatment emergent AEs leading to definitive treatment discontinuation
- Treatment-related TEAE
- Treatment-related TEAEs of grade ≥ 3
- Serious treatment-related TEAEs
- All TEAEs by primary SOC, HLGT, HLT, and PT, showing number (%) of patients with at least 1 treatment-emergent adverse event sorted by the SOC internationally agreed order. The other levels (HLGT, HLT, PT) will be presented in alphabetical order
- All TEAEs by primary SOC and PT, showing the number (%) of patients with at least 1 TEAE.
- Most frequent (5% of patients overall, on PT) TEAE by primary SOC and PT,
- All treatment-related TEAEs by primary SOC and PT, showing the number (%) of patients with at least 1 related TEAE.

Analysis of all treatment emergent serious adverse event(s)

- All serious TEAEs by primary SOC, HLGT, HLT, and PT, showing the number (%) of patients with at least 1 serious TEAEs, sorted by the internationally agreed SOC order. The other levels (HLGT, HLT, PT) will be presented in alphabetical order
- All serious TEAEs by primary SOC and PT, showing the number (%) of patients with at least 1 serious TEAE.
- All serious treatment-related TEAEs, by primary SOC and PT, showing the number (%) of patients with at least 1 serious related TEAE.

Analysis of all treatment-emergent adverse event(s) leading to treatment discontinuation

- All TEAE leading to definitive treatment discontinuation by primary SOC and PT, showing the number (%) of patients with at least 1 TEAE leading to treatment discontinuation.

A listing of patients with a TEAE leading to treatment discontinuation will be provided. This listing will include the TEAE, toxicity grade, relationship to study treatment and the day of occurrence.

Analysis of all treatment-emergent adverse event(s) leading to dose reduction

- All TEAEs leading to dose reduction by primary SOC and PT, showing the number (%) of patients with at least 1 TEAE leading to dose reduction.

Analysis of adverse events of special interest

- A listing of patients with at least one AESI cited in [Section 2.1.4.1](#) will be provided. This listing will include the category of AESI, the seriousness, the day of occurrence and the outcome.

Analysis of pre-treatment adverse events

- All pre-treatment AEs by primary SOC and PT, showing the number (%) of patients with at least 1 pre-treatment AE, sorted by the internationally agreed SOC order and decreasing incidence of PTs within each SOC.

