6.6 DOSE MODIFICATION

If a dose of IMP is vomited or omitted, the participant should not take the dose later or 2 doses at the next planned dose, and this information has to be recorded in the patient diary and eCRF.

Investigational medicinal product dose omission is allowed in case of severe toxicity and the reason should be documented in the eCRF. Doses omitted for toxicity are not to be replaced after the 14-day treatment period or compensated at the next planned IMP intake during the 14-day treatment period.

Conditions for dose modifications are aligned in [Table 3](#). Please refer to letrozole label information on additional specific contraindications and events requiring use precaution, and instruction of dose modification.

Table 3 - Dose modification for amcenestant arms and letrozole arm

NCI-CTCAE grade	Dose modifications
Grade 1 or 2	No dose adjustment required except for Grade 2 alanine transferase defined as an AESI *
Grade \geq 3	Amcenestant and letrozole should be definitely discontinued. No reintroduction is allowed.

NCI-CTCAE = National Cancer Institute Common Terminology Criteria for Adverse Events.

* See [Section 8.3](#)

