8.3 ADVERSE EVENTS AND SERIOUS ADVERSE EVENTS

Adverse event of special interest

An adverse event of special interest (AESI) is an AE (serious or nonserious) of scientific and medical concern specific to the Sponsor's product or program, for which ongoing monitoring and immediate notification by the Investigator to the Sponsor is required. Such events may require further investigation in order to characterize and understand them. Adverse events of special interest may be added, modified or removed during a study by protocol amendment.

- Pregnancy occurring in a female participant entered in the clinical trial. It will be qualified as an SAE only if it fulfills one of the seriousness criteria (see Appendix 3 [[Section 10.3](#)]).
 - In the event of pregnancy in a female participant, IMP should be discontinued.
 - Follow-up of the pregnancy in a female participant is mandatory until the outcome has been determined (See Appendix 4 [[Section 10.4](#)]).

- Symptomatic overdose (serious or nonserious) with IMP.
 - An overdose (accidental or intentional) with the IMP is an event suspected by the Investigator or spontaneously notified by the participant (not based on systematic pills count) and defined as at least twice the intended dose within the intended therapeutic interval, adjusted according to the tested drug.
 - Of note, asymptomatic overdose has to be reported as a standard AE.
- Increase in alanine transaminase (ALT) \geq Grade 2.
 - Liver function tests should be performed in patients with onset of otherwise unexplained nausea, jaundice, right upper abdominal pain, fever, or rash. LFTs include AST, ALT, ALP (isoenzymes if increase in ALP \geq Grade 3), total bilirubin (direct bilirubin if total bilirubin $>2 \times$ ULN), GGT, and INR (if total bilirubin $>2.5 \times$ ULN).
 - Discontinue study intervention in case of increase in ALT \geq Grade 2 if still on treatment, and repeat Liver function tests (LFTs) within 2-3 days. If not recovered, monitor LFTs weekly until recovery to Grade ≤ 1 (or baseline grade). Confounding factors such as, hepato-biliary disorders, concomitant medications, etc. should be excluded prior to study treatment discontinuation.
 - An ultrasound or other imaging in liver should be considered based on the clinical presentation.
 - A consultation with a hepatologist should be undertaken if there is,
 - unexplained or persistent increase in ALT \geq Grade 3 despite study treatment discontinuation.

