9.4.2.1 Analysis of adverse events

The observation period will be divided into 3 segments:

- The pre-treatment period is defined as the time from when the participants give informed consent to the first administration of the IMP.
- The on-treatment period is defined as the time from the first dose of IMP up to last dose of IMP.
- The post-treatment safety follow-up period is defined as the time from last administration of the IMP to the last administration of the IMP + 30 days.

Pretreatment AEs are defined as any AE occurring during the pretreatment period.

Treatment-emergent AEs are defined as AEs that develop, worsen (according to the Investigator's opinion), or become serious during

- on treatment period only, or
- the period including both the on-treatment and post-treatment period

All TEAE analyses will be produced for the two analysis periods as listed above. Pretreatment AEs will be described separately.

Treatment-emergent AEs will be coded according to MedDRA. Adverse events will be graded according to the NCI-CTCAE v5.0. The grade will be taken into account in the summary. For participants with multiple occurrences of the same PT, the maximum grade will be used.

An overall summary of TEAEs will be provided. The number and percentage of participants who experience any of the following will be provided:

- Treatment-emergent AEs
- Grade ≥ 3 TEAEs
- Grade 5 TEAEs (any TEAE with a fatal outcome during the on-treatment period)
- Serious TEAEs

- Treatment-emergent AEs leading to definitive treatment discontinuation
- Treatment-related TEAEs
- Treatment-related TEAEs Grade ≥ 3
- Serious treatment-related TEAEs.

Number and percentage of participants experiencing TEAEs by primary SOC and PT will be summarized by NCI-CTCAE v5.0 grade (all grades and Grade ≥ 3) for the safety population. Similar summaries will be prepared for treatment-related TEAEs, TEAEs leading to definitive discontinuation, TEAEs leading to dose modification, serious TEAEs, TEAEs with fatal outcome, AESIs, and AEs/SAEs occurring during the post-treatment period.

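### SAP 2.4.6.1 tabulates adverse events leading to dose reduction where the protocol requires dose modification, and it omits two other safety summaries that the protocol lists

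*SAP*

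**What the plan says.** **Protocol.** Section 9.4.2.1 sets out counts and percentages of participants with TEAEs by system organ class and preferred term. It then promises summaries of the same kind for further categories, including "TEAEs leading to dose modification, serious TEAEs, TEAEs with fatal outcome, AESIs, and AEs/SAEs occurring during the post-treatment period". The synopsis makes the same commitment.

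On changes to dosing, protocol 6.6 states that "Investigational medicinal product dose omission is allowed in case of severe toxicity", with the reason recorded in the eCRF. Its Table 3 then gives a rule by toxicity grade.

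**SAP.** Section 2.4.6.1 provides "All TEAEs leading to dose reduction by primary SOC and PT". It does not mention omission. Its AESI output is "A listing of patients with at least one AESI cited in" SAP 2.1.4.1, showing category, seriousness, day and outcome. TEAE tables are produced for two periods: on-treatment, and on-treatment plus the 30 days after the last dose. No table covers the post-treatment period alone.

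SAP 2.4.4, on exposure, treats a dose modification as either a reduction or an omission and counts patients with each.

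**The concern.** The protocol's category is modification and the SAP's is reduction. The SAP's own exposure section treats reduction as only one of two kinds of modification. The kind left out of the adverse event table is the one that the protocol names for toxicity.

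Safety in the three arms is a secondary objective, and the 200 mg arm is there to help choose the exposure for long adjuvant use. A reader comparing arms would look to this table for toxicity that interrupted dosing. If it is empty or nearly so, that reader could conclude that there was none, when the table was not set up to show it.

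The two other gaps are of the same kind. AESIs, which include photosensitivity and ALT increases, get no count by arm as a category. Surgery falls 1 (+1) day after the last dose, so perioperative events lie in the period that has no table of its own.

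**Working it through.** The point depends on no sample size, rate or error level, so the check is a comparison of text.

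**1. Which dosing changes for toxicity does the protocol contain?**
- Grade 1 or 2 (Table 3): "No dose adjustment required except for Grade 2 alanine transferase defined as an AESI".
- Grade 3 or higher (Table 3): "Amcenestant and letrozole should be definitely discontinued. No reintroduction is allowed".
- ALT of Grade 2 or higher (section 8.3): "Discontinue study intervention in case of increase in ALT" of that grade, if treatment is still ongoing.
- Text of section 6.6: omission in case of severe toxicity.

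No lower dose level is written for any arm.

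**2. Which of these does the SAP link to adverse events?**

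| Action | In the protocol for toxicity? | Table of TEAEs leading to it (SAP 2.4.6.1)? | Counted per patient elsewhere? |
|---|---|---|---|
| Definitive discontinuation | Yes | Yes: overview, SOC/PT table and patient listing | Yes, in disposition (SAP 2.2) |
| Omission | Yes | No | Yes, in exposure (SAP 2.4.4) |
| Reduction | No step defined | Yes | Yes, in exposure (SAP 2.4.4) |

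The last two rows are the mismatch.

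**3. Can the reduction table still receive an entry?** Yes, by several routes:
- SAP 2.4.4 counts as a reduction any dose below that of the previous day, or below the dose taken before an omission. Taking fewer than the planned four or two 100 mg capsules would qualify.
- Protocol 6.4 has a participant who takes one extra dose skip the next day. Return to the usual dose is then lower than the dose before the omission.
- Protocol 8.4 leaves modifications after an overdose to the investigator, in consultation with the medical monitor.
- Protocol 6.6 refers to the letrozole label for instructions on modification.

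So few or no entries are expected if the protocol is followed, but zero is not guaranteed.

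**4. Do the omission counts in SAP 2.4.4 fill the gap?** Only partly. They give patients with any omission, the number of omissions (0, 1, >1), and patients with at least 4 consecutive omitted days. They do not separate omissions by cause, so a forgotten dose and one withheld for an adverse event count alike.

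**5. Can post-treatment events be recovered by subtraction?** For any preferred term and arm, let n(on), n(post) and n(both) be the numbers of patients with the event on treatment, after treatment, and in both periods. The combined table shows

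n(combined) = n(on) + n(post) − n(both),

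so n(combined) − n(on) = n(post) − n(both). The difference counts only patients whose first such event came after treatment. It equals the promised figure only when n(both) = 0.

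**6. Are AESIs counted elsewhere?** ALT is summarised by grade and arm in the laboratory tables, with shift tables. Photosensitivity and symptomatic overdose, if reported as adverse events, appear under their preferred terms. None of these is a count by AESI category.

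**7. How many omissions for toxicity can there be?** SAP 2.4.4 defines an omission as a zero dose between two non-zero doses, so dosing must resume. If severe toxicity is taken to mean Grade 3 or higher (an assumption, since section 6.6 does not define the term), Table 3 stops treatment and bars reintroduction. Such a case could not then be an omission in the SAP's sense. Yet the text of 6.6 allows omission in just that situation. The two passages point in different directions, and the number of omissions linked to adverse events depends on how they are reconciled.

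**The case against.** The best counter-argument is that little is lost. Most toxicity-driven changes under Table 3 and section 8.3 are discontinuations, and the SAP reports these well. Omission is allowed only for severe toxicity, which largely overlaps the discontinuation rule, and treatment lasts 14 days. The untabulated group, patients who omitted a dose for an adverse event and then resumed, may be very small. The events themselves appear in the general TEAE tables. In a trial planned at 126 patients whose enrolment ended early, AESIs can be counted from a listing by hand.

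All of this stands as a limit on size. It does not remove the mismatch: the protocol promises three outputs that the SAP as written does not produce.

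A reader might infer three stronger things that the documents do not support:
- **That the reduction table must be empty, or will show 0% in every arm whatever the toxicity.** The routes in step 3 of the working leave entries possible.
- **That toxicity-driven changes to dosing go unreported.** Discontinuations are fully tabulated and omissions are counted by arm. Only the link between an adverse event and an omission is missing.
- **That the sponsor made an undisclosed change.** SAP 1.6 records major changes made in the amended SAP. It is not a log of differences from the protocol. The previous SAP version is not available here and may already have had the same wording, so silence in 1.6 proves nothing.

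**Conclusion.** The point holds as a mismatch between protocol and SAP with modest consequences. One protocol summary, TEAEs leading to dose modification, is narrowed to a category in which few or no entries are expected. Two others, AESI counts by arm and a post-treatment table of AEs and SAEs, are covered only in part. The impact is limited to descriptive secondary safety reporting; no primary estimate, population or interval changes.

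This rests on two assumptions: that the word reduction in SAP 2.4.6.1 carries the meaning given in SAP 2.4.4, and that sites follow Table 3. The number of patients affected cannot be derived from the documents and may be very small.

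**What to change.** In SAP 2.4.6.1:
- Replace *dose reduction* by *dose modification (omission or reduction, shown separately)* in the sub-heading and in the table.
- Add the number and percentage of patients by arm for each AESI category, and keep the listing.
- Add one table, by arm, of AEs and SAEs with onset in the post-treatment period.

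If the sponsor prefers not to produce any of these, the SAP should state the departure from protocol 9.4.2.1 and give the reason.

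Separately, the sponsor should reconcile the omission provision in the text of protocol 6.6 with the Grade 3 or higher row of Table 3, so that it is clear which adverse events can lead to an omission.

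The cost is a few lines of SAP wording and three standard tables. Protocol 6.6 already requires the reason for a toxicity omission in the eCRF, so no new data are needed, provided that this reason can be matched to the adverse event record. The eCRF layout is not in the documents, so this should be confirmed.
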